## Reasonable possibility:

According to the reporting investigator, there is a reasonable possibility (i.e., suggestive evidence or arguments) that there is a causal relationship irrespective of the dose administered between:

- The trial product (investigational product, active comparator, or placebo/vehicle, etc.) and the AE,
- The clinical trial protocol procedure (e.g. UV-induction, biopsy, xylocaine injection, blood test or intraocular pressure measurement, etc.) and the AE.

## No Reasonable Possibility:

No suggestive evidence or arguments can be identified regarding a causal relationship between the investigational product or the clinical trial protocol procedure and the AE.

### 8.2 PROCEDURES FOR REPORTING ADVERSE EVENTS

Adverse events will be collected from the time that a subject signs the ICF to his/her final trial visit.

At each visit, the investigator (or sub-investigator) will enquire about adverse events using an open question taking care not to influence the subject's answer (e.g., "Have you noticed any change in your health since the last visit?"). Direct questioning and examination will then be performed as appropriate.

GALDERMA RESEARCH & DEVELOPMENT Protocol N° RD.03.SPR.105061 Page 66 of 99 CONFIDENTIAL

Any AE occurring during the AE reporting period, whether it is related to the investigational product or not, will be recorded immediately in the source document, and described in the Adverse Event Form of the eCRF along with the date of onset, severity, relationship to the investigational products, and outcome, without omitting any requested and known information. Additional information may be requested under certain circumstances. Adverse Events assessed as related to the treatments will be monitored until they are completely or satisfactorily resolved. Other AEs will be monitored until the last visit if they are not resolved or satisfactorily resolved.

The investigator will obtain and maintain in the subject's files all pertinent medical records, information and medical judgment from colleagues who assisted in the treatment and follow-up of the subject. If necessary, the investigator will contact the subject's personal physician or hospital staff to obtain further details.

When an AE related to the treatment persists at the end of the clinical trial, the investigator will ensure the subject is followed up until the investigator and GALDERMA R&D agree that the event is satisfactorily resolved.

### 8.3 PROCEDURE FOR SUSPECTED ALLERGIC CONTACT REACTION

This is a general procedure and further details can be discussed with the sponsor.

- Stop the trial product.
- Take a picture of the affected area and the non-affected surrounding skin
- **Document the event and report it immediately** to the sponsor within 24 hours of receipt of the information as described in section 8.4.

# 8.3.1 In case of suspicion of allergic contact dermatitis

- 1. After all signs and symptoms have resolved and after a minimum of two weeks from last treatment application, perform a re-challenge test with the assigned trial product.
- 2. Ensure the subject has not been receiving any treatment with corticosteroids or antihistamines of any route of administration the week before testing.
- 3. Ensure that the skin on the back has not been exposed to the sun or artificial ultraviolet sources the week before testing.
- 4. Apply an appropriate quantity of the assigned trial product to fill the cupule of the test chamber on the skin of the upper back on either the right or left side of the centre line (or the inner forearm if the back cannot be tested). If no test chamber is available on-site, patch test units will be provided. It may be preferable to perform the test under semi-occlusive conditions depending on the irritant potential of the trial product and the intensity of the

reaction that was observed. The method to be used should be discussed with the sponsor. Choose a skin site that was not previously involved in the inflammatory skin reaction. Cover it for 48 hours with a hypoallergenic tape.

- 5. The subject should be informed about avoiding exercise, showers, application of toiletries, etc. to keep the test system dry
- 6. After 48 hours, remove the tests and evaluate the site:
  - at approximately 30 minutes after patch test removal (1st reading) and,
  - 24 to 48 hours later (i.e. 72 or 96 hours after application) (2nd reading).
  - A facultative 3rd reading may be performed 96 to 120 hours later (i.e. 6 to 7 days after application of the patch) if the overall assessment was equivocal or if requested by the sponsor.
  - Pictures of the tested areas will be taken systematically at each reading and properly documented.

Duration of trial product application	1st Reading	2nd Reading	3rd reading (optional)
48 hours	48 hours after trial product application (30 minutes after patch test removal)		6 or 7 days after trial product application (96 to 120 hours after patch removal)

7. Refer to the scoring system used by the International Contact Dermatitis Research Group (ICDRG) to assign a score at each reading (Spiewak, 2008):

Score	Morphology	Interpretation
-	No skin changes in the tested area	Negative
?	Faint, non-palpable erythema	Doubtful reaction
+	Palpable erythema (moderate edema or infiltrate), papules not present or scarce, vesicles not present	Weak positive reaction
++	Strong infiltrate, numerous papules, vesicles present	Strong positive reaction
+++	Erythema, infiltration, confluent vesicles, bullae or ulceration	Extreme positive reaction

ir	Inflammation sharply limited to the exposed area, lack of infiltrate, small petechiae, pustules, and efflorescences other than papules and vesicles	Irritant reaction
Nt		Not tested

8. At last reading, provide an assessment regarding a possible sensitization reaction using the following scale:

Sensitization Reaction		
0	Negative (absence of reaction or might be irritant reaction)	
1	Equivocal	
2	Positive	

- 9. Report the results from the re-challenge test as directed by the sponsor and document with photographs.
- 10. In case of absence of reaction, the subject may resume treatment if appropriate
- 11. If the re-challenge is positive or equivocal, notify the sponsor immediately. Except in specific situations, a new series of patch test will be initiated as directed by the sponsor (with individual ingredients at different concentrations if applicable, and possibly negative and positive controls) after a minimum of additional two weeks (but not later than 6 months) and after all signs and symptoms have resolved. The patch tests will be placed on the subject's back (or the inner forearm if the back cannot be tested) distant from the site of the re-challenge test (e.g., the left upper back skin if the re-challenge test was done on the right side). Follow the same procedure for the patch test as for the re-challenge.

# 8.3.2 In case of suspicion of immediate contact skin reaction (such as urticaria)

A case by case approach will be applied and the procedure to follow will be discussed with the sponsor.

### 8.4 PROCEDURE FOR REPORTING A SERIOUS ADVERSE EVENT

For any serious adverse event occurring during the clinical trial period, whether or not related to the treatment, expected or not, the investigator will:

- 1. Take prompt and appropriate medical action, if necessary. The safety of the subject is the main priority.
- 2. **Immediately (no later than 24 hours) inform the sponsor** of the event by fax/email, and discuss further steps to be taken:

	GALDERMA R&D
Name	
Title	
Address	
Tel. during office hours	
Tel. Outside office hours	
Fax	
Email	[contact]

The treatment allocation may be unblinded for the particular subject under either one or both of the following circumstances:

- If knowledge of the trial treatment is medically necessary in order to manage subject's safety,
- If GALDERMA pharmacovigilance decides that the event requires expedited reporting to the Regulatory Authorities and to the IRBs/ECs, whereby knowledge of the treatment allocation is necessary.
- 3. Complete the SAE Form provided by the CRA (Clinical Research Associate) at the start of the clinical trial (it is also available in the eCRF system as pdf document). Fax or send by email the completed form, accompanied by any other relevant information or anonymized medical records (e.g., laboratory test results) within 24 hours to the sponsor (see contact details above). The demographics, medical history, previous and concomitant therapies, and adverse event pages of the eCRF must be completed and available for review in the EDC system at the time of the report.
- 4. **Monitor and record the progress of the event until it resolves** or reaches a clinically stable outcome, with or without sequel. For all additional follow-up evaluations, fax or send by e-mail

GALDERMA RESEARCH & DEVELOPMENT Protocol N° RD.03.SPR.105061 Page 70 of 99 CONFIDENTIAL

all additional follow-up information on the SAE to the sponsor (see contact details above) within 24 hours of receipt of the updated information. SAEs will be monitored until the investigator and sponsor agree that the event is satisfactorily resolved.

- 5. Obtain and maintain in his/her files all pertinent medical records, information, and medical judgments from colleagues who assisted in the treatment and follow-up of the subject. If necessary, contact the subject's personal physician or hospital staff to obtain further details.
- 6. **Inform GALDERMA R&D of the final outcome of the event**. Send a revised or updated SAE Form, if appropriate (usually required every ten days) to the sponsor.
- 7. Comply with the applicable regulatory requirements related to the reporting of SAEs to IRB/EC.

#### 8.5 PROCEDURES FOR REPORTING PREGNANCIES

Any pregnancy occurring during clinical trials, where the foetus could have been exposed to the investigational products, must be followed-up until outcome in order to ensure the complete collection of safety data on GALDERMA R&D product.

In the case of a pregnancy of a clinical trial subject, the investigator will:

- 1. **Withdraw the subject from the clinical trial** and complete all appropriate visit evaluations and eCRF pages.
- 2. **Immediately (no later than 24 hours) contact the sponsor** to inform them of the pregnancy occurrence by fax/email and discuss further steps to be taken.

	GALDERMA R&D
Name	
Title	
Address	
Tel. during office hours	
Tel. Outside office hours	
Fax	
Email	[contact]

GALDERMA RESEARCH & DEVELOPMENT Protocol N° RD.03.SPR.105061 Page 71 of 99 CONFIDENTIAL

- 3. Complete, as fully as possible, the Pregnancy Surveillance Form Part I: History and start of pregnancy provided by the CRA at the beginning of the clinical trial (it is also available in the eCRF system as pdf document), and fax or send by email within 24 hours to the sponsor.
- 4. Monitor and record the progress of the pregnancy until its outcome. Contact the subject's regular physician (general practitioner or gynecologist) or hospital staff to obtain further details and ask regular follow-up information.
- 5. **Inform the sponsor of the progress by tri-monthly updates up** to the final outcome of the pregnancy. For all the additional follow-up evaluations, fax or send by e-mail the additional follow-up information to the sponsor within 24 hours of receipt of the information. If the subject can no longer be reached (lost to follow-up), documentation of the non-response/contact with two phone calls and a letter (certified with return receipt) is required.
- 6. At outcome of pregnancy, complete as fully as possible the Pregnancy Surveillance Form Part II: Course and outcome of pregnancy and send it by fax or by email to the sponsor within 24 hours following investigator's or site personnel becoming aware of the outcome of the pregnancy.
- 7. If the pregnancy leads to an abortion (voluntary abortion, spontaneous abortion or therapeutic abortion), *in utero* death or congenital anomaly, follow the procedure for declaration of an SAE (see section 8.4).
- 8. If the investigator is informed of a developmental abnormality of the baby, even a long time after the end of the clinical trial, he/she must inform the sponsor and follow the procedure for declaration of an SAE (see section 8.4).

#### 9 STATISTICAL METHODS PLANNED

#### 9.1 STATISTICAL AND ANALYTICAL PLANS

A Statistical Analysis Plan (SAP) will be developed as a separate document. The SAP will contain a more detailed and technical description of specific data conventions, calculations and of statistical procedures for executing the analyses that are specified in the sections of the clinical trial protocol below. The SAP will be finalized prior to database lock and unblinding. Any change made to the finalized SAP will be documented in the clinical trial report.

#### 9.1.1 Variables to be statistically analyzed

The following variables will be analyzed:

#### **Primary efficacy endpoint:**

• Total atrophic acne scar count per half-face at week 24

#### **Secondary efficacy endpoints:**

- Total atrophic acne scar count per half-face at each post-baseline visit (except week 24)
- Percent change from Baseline in total atrophic acne scar count per half-face at each post-baseline visit
- SGA per half-face at each post-baseline visit
- Investigator's preference on overall scar severity at week 12, week 24, early termination during part I
- Percent change from Baseline in total lesion count per half-face at each post-baseline visit
- Percent change from Baseline in inflammatory lesion count per half-face at each post-baseline visit
- Percent change from Baseline in non-inflammatory lesion count per half-face at each post-baseline visit.
- IGA per half-face at each post-baseline visit

#### **Exploratory efficacy endpoints:**

- *Investigator's assessment of skin roughness* of each half-face at Baseline, week 12, week 24, week 48, early termination
- *Investigator's assessment of skin texture change* per half-face at week 12, week 24, week 48, early termination
- *Skin microrelief variables:* percent change from Baseline per half-face at week 24, week 48, early termination (if early termination occurs after week 8)

GALDERMA RESEARCH & DEVELOPMENT Protocol N° RD.03.SPR.105061 Page 73 of 99 CONFIDENTIAL

#### Safety endpoints:

- Incidence of adverse events
- Local tolerability: percent of subjects across scores at each post-baseline visit

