### 6.4 DOSE MODIFICATION

Local cutaneous reactions including erythema, scaling, dryness, and stinging/burning may be experienced with use of Adapalene 0.3% - BPO 2.5% gel. All these adverse reactions are easily managed depending upon the severity of these adverse reactions.

Patients should be instructed to use a moisturizer (if possible the one provided for this trial) and if needed, investigators may reduce temporarily the frequency of the application of Adapalene 0.3% - BPO 2.5% gel (eg. every other day), or temporarily discontinue use. In such cases, the treatment on both half-face should be suspended, even if the irritation is only on one half-face.

These are most likely to occur during the first four weeks of treatment but are mostly mild to moderate in intensity, and usually improve with continued use of the medication.

GALDERMA RESEARCH & DEVELOPMENT Protocol N° RD.03.SPR.105061 Page 52 of 99 CONFIDENTIAL

All dose modifications will be documented in the subject's source data and reported in the eCRF (treatment compliance page).

In addition, for part II, at visits Week 36 and Week 48, any dose modification for safety reasons should lead to the collection of additional information (date of onset and resolution, diagnosis, severity, seriousness and treatment(s) if any). The Sponsor should be notified by email ([contact]) within 24 hours after being informed of this dose modification for safety reasons.

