#### 9.1.2.4 Missing values

The last observation carried forward (LOCF) method will be used to impute missing values of acne scar and lesion counts and global assessment scores (SGA and IGA) during part I. If no post-baseline data are available, baseline will be carried forward. The other missing values of part I and the data collected during part II will not be replaced (observed data).

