#### 9.1.4 Statistical analyses

The primary objective of this trial is to demonstrate the superiority of Adapalene 0.3% - BPO 2.5% gel compared to its vehicle, in terms of total atrophic acne scar count at week 24. The mean bilateral difference between products of primary efficacy endpoint will be analyzed by using the Wilcoxon Rank Signed test, testing the hypothesis of equality. The p-value will have to be inferior to 0.05 at week 24, on ITT/LOCF population. Per Protocol analysis will be also performed to assess the robustness of the results obtained on the ITT/LOCF population.

GALDERMA RESEARCH & DEVELOPMENT Protocol N° RD.03.SPR.105061 Page 75 of 99 CONFIDENTIAL

The other efficacy variables of part I will be analyzed similarly as the primary analysis on the appropriate population. Each test will be two-sided, at the 0.050 significance level.

The subject characteristics (previous medication, concomitant medication, demographics, baseline characteristics...), lesion counts, microrelief, adverse events, local tolerability and questionnaires and all variables of part II will be summarized by descriptive statistics (usual statistics and frequency distribution).

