5.4 MISSING VALUES

In order to evaluate the effect of major deviations or of data exclusions, the last observation carried forward (LOCF) method will be used to impute missing values of acne scar and lesion counts and global assessment scores (SGA and IGA). If no post-baseline data are available, baseline will be carried forward. Thus, the number of subjects will not vary at each visit. The other missing values will not be replaced (observed data).

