14.3.3. Local Tolerance

Table 57. Erythema score by visit, Descriptive (APT)

	ABPO Forte	Vehicle
Baseline		
None		
Mild		
Moderate		
Severe		
Mean±SD		
Median		
(Min,Max)		
Week 24		
None		
Mild		
Moderate		
Severe		
Mean±SD		
Median		
(Min,Max)		

Table 58. Scaling score by visit, Descriptive (APT)

Table 59. Dryness score by visit, Descriptive (APT))

Table 60. Stinging/Burning score by visit, Descriptive (APT)

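### Local tolerability is tabulated only visit by visit on observed scores, so the tables cannot show who ever had moderate or severe irritation and are likely to understate it on the active side

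*Protocol*

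**What the plan says.** Protocol 9.1.1 (safety endpoints) gives local tolerability as the "percent of subjects across scores at each post-baseline visit", and SAP 4.3 repeats this per half-face. Protocol 9.1.4 makes the summary descriptive. SAP 14.3.3 has one table for each of the four signs (Tables 57 to 60), with score categories and usual statistics at each visit in an active and a vehicle column. None has a row for the number scored, a worst score over visits, a bilateral difference, or a mark for treatment status. SAP 6.5 gives methods for exposure and adverse events, and none for tolerability.

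Carrying forward is limited to scar and lesion counts, SGA and IGA. For everything else SAP 5.4 says "The other missing values will not be replaced (observed data"), and protocol 9.1.2.4 agrees.

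Protocol 6.4 expects irritation mainly in the first four weeks. Moisturizer comes first. If needed, the investigator may lower the frequency or stop for a time, and then "the treatment on both half-face should be suspended, even if the irritation is only on one half-face". The record is kept: "All dose modifications will be documented in the subject's source data and reported in the eCRF (treatment compliance page"). SAP 6.2.7 draws on that page for compliance, which Table 12 shows in four classes, the top one being 75% or more. SAP 6.5.1 counts exposure from first to last use.

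Under protocol 7.2.1, irritation becomes an adverse event if treatment is stopped for good, if it needs a drug other than moisturizer, or if it interrupts participation after the week 4 visit. Protocol 8.1.1 also names interruption, but without the week 4 limit.

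**The concern.** Application-site irritation is the reaction the protocol itself links to the active gel (2.3.2), and every subject carries a vehicle control on the other half-face. The natural safety question is what share of subjects ever had a moderate or severe sign on the active side, and what share on the vehicle side. A row of visit columns cannot answer it. The columns cannot be added, because one subject may count in several, and the largest column is only a lower bound.

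The outcome can also change what is measured. A subject whose gels are reduced or suspended because of irritation may be scored at the next visit on skin that is not under treatment. A subject who leaves drops out of later columns. Both effects lower the percentages shown for the side that irritates more. What is at stake is the descriptive tolerability statement, not the primary test.

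**Working it through.** The documents give no rate for irritation, suspension or exit, so there is no plan figure to reproduce. The check follows one subject through the records, then shows ranges under stated assumptions.

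**1. A subject irritated in week 2 who suspends and recovers before week 4.** The part I visits near this time are weeks 1, 4 and 8 (protocol 5.1).

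| Record | Does it show the episode? |
|---|---|
| Erythema, scaling, dryness (Tables 57-59) | No: scored at weeks 1 and 4 only |
| Stinging/burning (Table 60) | Possibly: 7.2.1 asks about earlier application days |
| Adverse event tables | Not required by 7.2.1 (before the week 4 visit); required by 8.1.1 if the suspension counts as an interruption of participation |
| Table 12 | Only as lower compliance, within broad classes |
| Exposure (Table 45) | No: suspended days count as exposure |

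**2. Leavers and the denominator.** Of 60 enrolled, let e leave because of irritation and let x of the rest be irritated at a later visit. The later column shows x/(60 − e); the share ever irritated is (x + e)/60, if nobody else was affected. The largest e used is 12, the whole of the roughly 20% exclusion allowance (protocol 9.2.2).

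| e | x | Later column | Ever irritated |
|---|---|---|---|
| 3 | 0 | 0% | 5% |
| 6 | 6 | 6/54 = 11.1% | 12/60 = 20% |
| 12 | 6 | 6/48 = 12.5% | 18/60 = 30% |

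**3. The week 4 column.** Assumptions: 20% of subjects are ever moderately or severely irritated on the active side; onset is uniform over days 1 to 28 (27 days); an episode lasts 21 days if treatment continues and 5 if it is suspended; visits fall on days 7 and 28. Among irritated subjects a share s is suspended and a share q leaves at onset.

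- No suspension or exit: week 4 = 0.20 × 21/27 = 15.6%.
- With an exit assessment scored as irritated: 0.20[(1 − s)·21/27 + s·5/27] / (1 − 0.20·q·6/27).
- Without one: 0.20[(1 − s − q)·21/27 + s·5/27] / (1 − 0.20q).
- Worst recorded score: 0.20[(1 − s) + s·10/27] with an exit assessment; 0.20[(1 − s − q) + s·10/27] without.

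| s | q | Exit assessment | Week 4 column | Worst recorded score |
|---|---|---|---|---|
| 0 | 0 | n/a | 15.6% | 20.0% |
| 0.3 | 0.1 | yes | 12.1% | 16.2% |
| 0.3 | 0.1 | no | 10.7% | 14.2% |
| 0.5 | 0.2 | yes | 9.7% | 13.7% |
| 0.5 | 0.2 | no | 6.8% | 9.7% |

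With 10% ever irritated, the week 4 column falls from 7.8% to between 3.3% and 6.0%; with 30%, from 23.3% to between 10.4% and 18.1%. In every row with suspensions or exits the worst recorded score also stays below the true share, so that row alone is not enough.

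**4. What Table 12 can show.** If compliance counts days of use over 24 weeks (168 days), alternate-day use for four weeks loses 14 days: (168 − 14)/168 = 91.7%. The top class holds down to 0.75 × 168 = 126 days, so up to 42 missed days stay in it.

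**The case against.** The strongest case against is that by-visit scores per half-face, together with adverse events by treated side, are a coherent presentation for a phase IV trial whose main objective is scar formation. Much of this stands.

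- A reader might infer that the worst-affected subjects are scored off treatment as a rule. Protocol 6.4 makes any dose change discretionary, so this is possible, not certain. It also says that reactions usually improve on continued use, so low later scores may be genuine recovery.
- A reader might infer that leavers vanish. They should have the next scheduled visit's procedures, tolerability included, whenever possible (protocol 4.4 and 5.5.8). A permanent stop for irritation is an adverse event, and Table 56 shows discontinuations by side. Leavers are missing only from later columns of Tables 57 to 60.
- A reader might infer that the dose-modification records go unused. They feed compliance in SAP 6.2.7 and Table 12, though coarsely.
- Stinging/burning looks back to application days, so the gap is mainly in the other three signs.
- Visit spacing misses vehicle-side episodes of equal length in the same proportion, so spacing alone shrinks the absolute difference but not the ratio between sides.

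What the objection does not reach is the absence of any summary over visits, and the period before the week 4 visit. Irritation is expected mainly then, and 7.2.1 does not require an interruption to be an adverse event.

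**Conclusion.** The point holds as a cheap improvement to reporting. Tables 57 to 60 cannot give the share of subjects who ever had moderate or severe erythema, scaling or dryness on either side, and they are likely to understate it on the active side. The direction rests on irritation being more frequent under the active gel and on some subjects being suspended or leaving because of it. The size cannot be derived from the documents: the percentages above depend on assumed rates, onset and duration. They do not support a claim that the safety report as a whole is biased, or biased by a known amount. Separately, protocol 7.2.1 and 8.1.1 disagree on whether an early interruption is an adverse event, and must be reconciled. The primary analysis is untouched.

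**What to change.** In SAP 4.3, 6.5 and 14.3.3:

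- Keep Tables 57 to 60 and add the number scored at each visit.
- For each sign, add the worst post-baseline part I score per half-face (active, vehicle and within-subject difference), using all visits including early termination.
- Flag scores taken while treatment was reduced or suspended; the daily tablet log and the eCRF compliance page are the sources.
- Tabulate subjects with at least one safety-driven reduction or suspension, before and after the week 4 visit.
- Optionally, report exposure net of suspended days beside first-to-last-use duration.

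Reconcile protocol 7.2.1 with 8.1.1 on interruptions before the week 4 visit.

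The cost is some SAP wording and a few tables, with no extra site work provided the compliance page holds the dates and reasons of dose changes. The documents do not show that page, so this should be confirmed. The irritation figures for the active gel will probably look less favourable, and the worst-score row will recover only part of what is missed, which is why the count of reductions and suspensions belongs beside it.
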